## Statistical Methods

### Sample size determination

Power Analysis will be conducted for determination of the Sample Size of this study, in order to estimate a Sample Size that is required so that the study would have adequate power to detect clinically meaningful differences between the two groups, especially concerning Lung Compliance (which is the primary outcome of the study).

For this analysis, we used G\*Power Software (version 3.1.9.2), which is freely available at <http://www.gpower.hhu.de/en.html> from the Heinrich-Heine-Universität of Dusseldorf.

Our Power Analysis is based on a published study in literature, from Manner et al. Assuming that Clinically meaningful difference between the two groups is 20% of the mean value and SD of the observed Lung Compliance is 15% of the mean value, therefore Size effect = 0.2 /

0.15 = 1.33, with two-sided testing, with alpha = 0.05 and power = 0.9 (therefore,  $b = 1 - \text{power} = 0.1$ ). Under these assumptions, G\*Power calculated that we will need minimum 13 patients in each group (totally, 26 subjects) for this study to have adequate power.

Assuming a 15% drop-out rate of the initial number of subjects enrolled to this trial, total number of **30** patients will have to be randomized

Alternatively, using the adequate mathematic formula (see Appendix 2) and the results from the Manner et al study, we confirm a minimum Sample Size of 26 patients.

### Statistical Analysis

[figure not shown]
Investigators will assess data for normality (using Kolmogorov Smirnov and Shapiro Wilks test). Ventilatory and hemodynamic data and intraoperative and postoperative variables (all continuous variables) will be presented as mean values (+/- SD). Data will be compared between and within groups using Mixed Analysis of Variance (Mixed Anova - General Linear Model) if are normally distributed or with Kruskal Wallis test in case that we do not have normally distributed data. Bonferroni correction will be used for multiple comparisons correction. In order to check and supplement our Mixed Analysis of Variance we will also use two-sample t-test to compare the two groups at each time point (for ventilatory and hemodynamic variables). Patient and procedural characteristics will be compared between groups using independent-sample t-test for continuous variables and chi-square test for categorical variables. Two tailed P-values < 0.05 will be considered statistically significant. For data analysis, the investigators will use SPSS statistical software (version 22).

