### Results and Discussion

Data will be presented as mean value (+/- SD) and  $p < 0.05$  will be considered significant. The investigators will use Mixed Analysis of Variance to make comparisons between and within groups. At time points before RM is performed, there should be no significant differences in Lung Compliance between the two groups ( $p > 0.05$ ). The investigators will use two-sample t-test as supplementary analysis in order to compare the two groups at each time point, while chi-square test for categorical variables and two-sample t-test for continuous variables for patient and procedural characteristics differences between the two groups will be used. In the RM group, according to similar studies, we expect to detect a significant increase in lung Compliance after RM in comparison to control group where RM will not be applied. In the RM group, the investigators estimate that Dynamic Lung Compliance will be significantly increased compared to baseline compliance too. There should be no significant differences in demographics between the two groups. The investigators expect that there will be no statistical or/and clinical significant differences in patients' hemodynamics and blood gas measurements.

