### Inclusion Criteria

Children aged between 1-14 years who are scheduled for elective Abdominal Laparoscopy will be eligible for this study.

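### The trial is sized for one two-group comparison of compliance, but the lead analysis is a Mixed ANOVA over eight time points, only one of them after the recruitment maneuver, with no deciding term named

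*Protocol*

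**What the plan says.** **Sample size.** Protocol, Sample size determination, assumes that the "Clinically meaningful difference between the two groups is 20% of the mean value" and that the "SD of the observed Lung Compliance is 15% of the mean value", "with two-sided testing, with alpha = 0.05 and power = 0.9". This yields a "minimum 13 patients in each group (totally, 26 subjects"), raised to 30 randomised. Appendix 2 describes the calculation as one for two independent means. It contains no repeated measures and no covariate.

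**Analysis.** Protocol, Statistical Analysis: "Data will be compared between and within groups using Mixed Analysis of Variance (Mixed Anova - General Linear Model"). A Bonferroni correction follows, without a stated family. Then, as a check and supplement, "we will also use two-sample t-test to compare the two groups at each time point". The Abstract also calls the t-tests supplementary, so the Mixed ANOVA leads. Neither place names the ANOVA term that decides, and neither uses a pre-RM value as a covariate.

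**Endpoint and time points.** The Primary endpoint section names improvement in dynamic compliance without a time point or contrast. Appendix 4 has eight compliance columns: T1, T2, T2c, T3, T3c, T4, T4c and T5. In Time points of measurements, T5 is the only one of these defined as following the RM. The Abstract expects the groups to be alike until then: "At time points before RM is performed, there should be no significant differences in Lung Compliance between the two groups". Efficacy and Safety Issues sets the clinical threshold at a 20% increase in weight-corrected mean compliance.

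**The concern.** The RM can affect only the T5 compliance value. A Mixed ANOVA over all eight points offers two terms that involve group, and neither is the T5 contrast for which the trial was sized. The group main effect averages the T5 difference with seven differences whose expected value is zero. The group-by-time term is an omnibus test on 7 degrees of freedom. It responds to any departure from parallel profiles, and it gives no estimate to set against the protocol's 20% threshold. The comparison that was powered, T5 between groups, appears only as one of eight supplementary t-tests, possibly at a Bonferroni-reduced level.

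At stake is whether the 90% power that justified 26 evaluable children carries over to the analysis that will be reported, and whether the trial yields an interpretable effect size.

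**Working it through.** **Inputs from the protocol.** Difference 0.20 and SD 0.15 (both as fractions of the mean), two-sided alpha 0.05, 13 per group, eight compliance points, effect at T5 only.

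**Assumptions.** The protocol gives no within-patient correlation ρ. I take 0.5 to 0.9, either equal between all pairs of points (compound symmetry) or decaying with distance (AR(1)). The 15% SD is taken to apply to the weight-corrected value at every point.

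**1. The plan's own figure.** d = 0.20/0.15 = 1.333. For an unpaired t-test with n per group, the noncentrality is d·√(n/2) = 1.333 × √6.5 = 3.40 on 24 df. Power is 90.3% with 13 per group and 87.7% with 12. The stated 13 per group is reproduced, for one unadjusted comparison.

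**2. Group main effect.** The difference in eight-point means is 0.20/8 = 0.025. Under compound symmetry the SD of a patient's mean is 0.15·√((1+7ρ)/8).

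- ρ = 0.5: SD 0.1125, d = 0.222, power 8.5%
- ρ = 0.7: SD 0.129, d = 0.194, power 7.6%
- ρ = 0.9: SD 0.143, d = 0.174, power 7.1%

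Under AR(1), simulation gives 11.8%, 8.7% and 6.9%.

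**3. Group-by-time test (7 df) and T5 ANCOVA.** Simulated power, 13 per group, 2,000 runs per setting:

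| Structure, ρ | Interaction, uncorrected | Interaction, Greenhouse-Geisser | ANCOVA on T4c | ANCOVA on T1 |
|---|---|---|---|---|
| Compound symmetry 0.5 | 92.5% | 88.9% | 96.0% | 96.5% |
| Compound symmetry 0.7 | 99.7% | 99.5% | 99.3% | 99.4% |
| Compound symmetry 0.9 | >99% | >99% | >99% | >99% |
| AR(1) 0.5 | 69.6% | 57.4% | 95.4% | 88.5% |
| AR(1) 0.7 | 80.0% | 63.6% | 99.7% | 89.8% |
| AR(1) 0.9 | 99.7% | 96.5% | >99% | 94.8% |

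**4. T5 t-test with Bonferroni over eight points.** Alpha = 0.05/8 = 0.00625. Power is 65.5% with 13 per group and 74.9% with 15. Uncorrected, it is 90.3% and 94.1%.

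**5. Balance by p-value.** With no true difference and compound symmetry, at least one of the seven pre-RM t-tests gives p < 0.05 in 24.7% of simulated trials at ρ = 0.5 and 18.0% at ρ = 0.7 (3,000 runs). Such a result would be chance, not a failure of randomisation.

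**The case against.** **The main effect may not be meant.** A reader might infer that the trial as planned has 7 to 8% power. The documents do not support that, because they never say the group main effect decides. The stated expectation is a rise after the RM relative to control, which in a Mixed ANOVA is most naturally the group-by-time term. That term keeps good power when correlation is high or roughly equal across points. This stands, and it limits the claim: the low figure belongs to one permitted reading. The interaction still falls to 57% under plausible decaying correlation, and it still yields no estimate.

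**Multiplicity is addressed.** A reader might infer that eight t-tests inflate the false-positive rate for the RM claim. The protocol plans a Bonferroni correction and ranks the t-tests as supplementary. A difference at any of the seven pre-RM points could not support an RM effect. This stands too. What remains is that the family is undefined, and if it is the eight points, T5 power drops to about 66%.

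**Missing Trendelenburg readings.** A reader might infer that children will be lost from a complete-case model. The protocol admits a broad population ("Children aged between 1-14 years who are scheduled for elective Abdominal Laparoscopy will be eligible for this study"), and T3 and T3c presuppose Trendelenburg positioning. It does not say that any child will not be tilted, and it provides last-observation-carried-forward in its intention-to-treat branch. This is a possibility, not a finding.

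**ANCOVA is not required for validity.** An unadjusted T5 comparison is unbiased under randomisation and has the planned 90%. Adjustment is an improvement, not the repair of a bias.

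**The SAP may settle this.** It may, but the protocol itself names a lead analysis that differs from the comparison it was sized for.

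**Conclusion.** The point holds as a mismatch between the sample-size comparison and the lead analysis, with the deciding term left open. At the planned effect with 13 per group, power depends on which test is taken as decisive: about 7 to 8% (main effect, compound symmetry; up to about 12% under AR(1)), 57 to 100% (Greenhouse-Geisser interaction), 66% (T5 with Bonferroni over eight) or 90% (single T5 t-test). A T5 ANCOVA on T4c has about 95% to over 99%. On T1 it has the same range under compound symmetry, but about 88 to 95% under AR(1).

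These figures rest on the assumed correlations of 0.5 to 0.9, and on T5 being the only post-RM compliance value. The second condition follows from Time points of measurements and End of Treatment. Blinding Procedure, however, places T4 after the point at which the RM is or is not given, and Time points does not explicitly time T4c against the RM. These sections must be reconciled. The sample size itself need not change.

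**What to change.** 1. State one primary analysis: the between-group difference in weight-corrected dynamic compliance at T5, by ANCOVA with a pre-RM compliance value as covariate, at two-sided alpha 0.05. Report the adjusted difference with a 95% confidence interval and read it against the 20% threshold.
2. Reconcile Time points of measurements, End of Treatment and Blinding Procedure on whether T4 and T4c precede the RM. State also whether T4c is recorded before the allocation envelope is opened. If T4c is confirmed as a pre-RM value, use it as the covariate; otherwise use T1.
3. Make the Mixed ANOVA and the comparisons at other time points descriptive. Bonferroni then has no bearing on the primary test.
4. Remove the use of non-significant pre-RM or demographic p-values as evidence of balance, and describe baseline values instead.

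The cost is protocol and SAP wording. T1, T4c and T5 are already collected and no additional patients are needed. If some children turn out not to be placed in Trendelenburg, the primary model no longer depends on T3 and T3c, so they are not lost from it.

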## Randomization

In order to perform Randomization, the investigators will use web-software-generated blocks (available at: <http://www.randomization.com/>). Patients will be randomized to one of the two Ventilation Management Groups (RM or Control group) with 15 patients per group. Each patient assigned to participate in the study will have a sequentially numbered (from 1 to 30) sealed envelope containing Randomization Code (A or B). The Principal Investigator will be the only person who will be aware of the correspondence between Codes and study Groups. The envelopes will be concealed until deflation of pneumoperitoneum, just prior to application of RM (or not). All operations will be performed by the same team of surgeons and by the same anesthesiologists (PI and Second Investigator). In Appendix 1, there is an example of performed permuted blocks randomization with 30 patients, created by this web-software.

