## Time points of measurements

After a stabilization period of 1-2 minutes of Mechanical Ventilation (stabilization defined as a stable Vt for at least 4 consecutive breaths), the above parameters (except Blood gas measurements – see Appendix 6) will be measured at the following time points:

T1	Baseline	After tracheal intubation and ventilation stabilization, with the patient in the supine position and before surgical incision
T2	Pneumoperitoneum	After insufflating CO 2 to the defined IAP
T2c	Correction	After adjusting PIP to return Vt to 6-7 ml/kg IBW or within 10% of baseline
T3	Trendelemburg	After Trendelemburg positioning
T3c	Correction	After Trendelemburg positioning and after adjusting PIP to return Vt to 6-7 ml/kg IBW or within 10% of baseline
T4	Deflation	After completing the laparoscopic procedure with the patient returned to the supine position with the abdomen deflated
T4c	Correction	Post-deflation correction, after returning PIP to baseline
T5	After RM / Before Reversal of Neuromuscular Blockade	3 minutes after RM in the RM group and before the reversal of neuromuscular blockade and Extubation in both groups
T6	Post-operative	30 min after the admission in PACU

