## Efficacy and Safety Issues

The efficacy of the RM to improve  $Com_{dyn}$  and gas exchange is the main issue of this study. The investigators regard that  $Com_{dyn}$  will be statistically significantly improved in the RM group compared to Control group. In this study, we consider clinically significant a 20% increase in the weight corrected mean  $Com_{dyn}$  in the RM group.

This improvement in lung compliance maybe would not be clinically significant, as our study population consists of healthy children (children with ASA I-II classification). Nevertheless, the possibility of underlying comorbidities should always be taken into account and anesthesia in addition to these comorbidities could negatively influence cardiovascular and pulmonary function, and thus patients' outcome. This is the reason that ventilation strategy adopted in this study has a protective-lung ventilation strategy orientation, with lower  $V_t$  and higher PEEP than usual in clinical practice the past years.

The investigators regard that there would be statistical significant difference within RM group, as well.  $Com_{dyn}$  is expected to be significantly improved in post-RM measurements in comparison to baseline  $Com_{dyn}$ , for the patients of RM group. A 20% increase in  $Com_{dyn}$  would be clinically significant too.

Secondarily, the investigators regard that RM will improve post-RM intra- and post-operative  $PO_2$  and ratio  $PO_2/FiO_2$ . For the population of this study (children ASA I-II), this improvement may also not have a clinically significant impact.

Although recruitment procedures are generally well tolerated with few adverse effects, there are several potential complications that could occur.

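### The Kruskal-Wallis fallback for non-normal data is the wrong test for within-patient comparisons and cannot test group-by-time, although it is valid between the two groups at a single time point

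*Protocol*

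**What the plan says.** The Statistical Analysis section begins with a check on the trial's own data: "Investigators will assess data for normality (using Kolmogorov Smirnov and Shapiro Wilks test". It then states the main method, "Data will be compared between and within groups using Mixed Analysis of Variance", for normally distributed data, "or with Kruskal Wallis test in case that we do not have normally distributed data" otherwise. One sentence therefore gives both methods the same task. The Abstract describes that task in the same way: "The investigators will use Mixed Analysis of Variance to make comparisons between and within groups". No paired or repeated-measures rank test is named. The supplementary two-sample t-tests at each time point are parametric and compare groups only.

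The data are repeated measurements. Under Time points of measurements the parameters "will be measured at the following time points". Appendix 4 has eight columns for compliance (T1 to T5, including the corrected readings), and Appendix 5 adds T6 for hemodynamics.

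Efficacy and Safety Issues sets two hypotheses. One compares the RM group with Control. The other lies within the RM group, where compliance "is expected to be significantly improved in post-RM measurements in comparison to baseline". On size, the Randomization section says: "Patients will be randomized to one of the two Ventilation Management Groups (RM or Control group) with 15 patients per group".

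**The concern.** Kruskal-Wallis is a test for independent samples. It has no term for the patient, so it cannot use the pairing of a child's later value with that child's own baseline. It also has no interaction term, so it cannot ask whether compliance changed differently over time in the two groups. A Mixed ANOVA does both.

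If the fallback is used, the within-RM-group hypothesis is tested by a method that leaves the large differences between children in the error. The true error rate then falls far below the nominal 5% and power falls with it, so a real improvement of moderate size could be reported as not significant. The group-by-time question would have no test at all. This is a method the Protocol has fixed, not a detail left open for a later plan.

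**Working it through.** **Inputs.** From the Protocol: 15 per group; eight compliance time points; two-sided alpha 0.05; and the sizing assumption "difference between the two groups is 20% of the mean value and SD of the observed Lung Compliance is 15% of the mean value". Not in the Protocol: the within-patient correlation ρ. I assume 0.3 to 0.8 and take it as equal for all pairs of time points.

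**The Protocol's own figure.** Effect size = 0.20 / 0.15 = 1.33. The noncentral t distribution gives power of 87.7% at 12 per group and 90.3% at 13, so the stated minimum of 13 per group (26 in total) reproduces. It concerns a two-group comparison and does not depend on the fallback. I use it only for the 1.33 SD effect.

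**Step 1: between groups at one time point.** With two groups, Kruskal-Wallis is the rank-sum test. Simulated at T5 with 15 per group and skewed data (CV about 15%), it rejects a true null in 5 to 6% of trials. At 1.33 SD its power is 93%, the same as the t-test. This part of the fallback works.

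**Step 2: two time points within one group, no true change.** The variance of the mean paired difference is 2σ²(1 − ρ)/n. A test that ignores pairing assumes 2σ²/n. In large samples its actual level is therefore about 2Φ(−1.96/√(1 − ρ)):
- ρ = 0.3: 1.96/0.837 = 2.34, level 1.9%
- ρ = 0.5: 1.96/0.707 = 2.77, level 0.6%
- ρ = 0.8: 1.96/0.447 = 4.38, level about 0.001%

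Simulating Kruskal-Wallis itself with n = 15 gives about 2%, 1% and 0.1%. Across all eight time points within a group the null rejection rate is about 0.9% at ρ = 0.3, 0.1 to 0.2% at 0.5 and 0% at 0.8. Friedman's test holds 3.7 to 4.4% over the correlations tried.

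**Step 3: power for a paired shift within one group of 15** (normal and lognormal data agree closely)

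| ρ | 0.5 SD: Kruskal-Wallis | 0.5 SD: signed-rank | 1.33 SD: Kruskal-Wallis | 1.33 SD: signed-rank |
|---|---|---|---|---|
| 0.3 | 21% | 30% | 96% | 97–98% |
| 0.5 | 20% | 44% | 97–98% | 99–100% |
| 0.8 | 13% | 79% | 99% or more | 100% |

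The 0.5 SD shift is my assumption; 1.33 SD is the Protocol's.

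**Step 4: group-by-time.** Suppose the groups differ by a constant 1 SD at every time point, so that there is no group-by-time effect (ρ = 0.5 and 0.7). Kruskal-Wallis at T5 rejects in 73% of trials. A rank-sum test on each child's change from T4c to T5 rejects in 4 to 5%. Kruskal-Wallis therefore does not isolate a difference in change.

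**The case against.** The strongest reply is that the main comparison is RM against Control, that the trial was sized on it, and that at T5 the fallback is a valid test with adequate power. This stands. Under randomization a T5 comparison needs no interaction term to be valid, so the main between-group claim is not undermined.

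A second reply is that at the Protocol's own effect the within-group loss is small. This also stands: Step 3 shows a difference of at most a few points at 1.33 SD, and Kruskal-Wallis across all eight time points still detects a 1.33 SD rise at T5 in 85 to 89% of trials (ρ = 0.8 and 0.5). The loss matters for effects smaller than the one planned.

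A third reply is that the fallback may never be used. The Protocol gives no compliance distribution, and weight correction deals with part of the spread in size, so I do not claim that it is likely to be triggered.

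A reader might also infer gross false-positive inflation. If all eight time points were stacked as independent rows, the variance of a group mean would be understated by a factor of 1 + 7ρ. The level would then be about 2Φ(−1.96/√(1 + 7ρ)): 27% at ρ = 0.3 (factor 3.1), 36% at 0.5 (4.5) and 45% at 0.8 (6.6). Simulation gives 26 to 47% for ρ from 0.3 to 0.9. The Protocol nowhere prescribes such pooling. Its time points are distinct surgical phases, and its supplementary tests are run at each time point. The figure describes a misuse to rule out, not the plan.

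None of these replies covers the within-group part, which the sentence names expressly.

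**Conclusion.** The concern holds in a limited form. As written, the fallback is correct between the two groups at a single time point, wrong for comparisons within patients, and unable to test group-by-time.

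The within-group error is towards missing effects, not towards false claims: a true level of about 0 to 2% instead of 5%, with a marked loss of power for moderate shifts and a small one at 1.33 SD. These sizes rest on an assumed equal correlation of 0.3 to 0.8 and on 15 patients with complete data. The direction is the same for any positive correlation.

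The documents do not support reading this as a failure of the primary between-group comparison, as inflated false positives under the stated plan, or as a reason to change the sample size.

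**What to change.** Replace the Kruskal-Wallis clause with named tests for each question:
- Within-group change (for example T5 against T1 in the RM group): Wilcoxon signed-rank, or Friedman where several time points are compared together.
- Between groups at T5: Wilcoxon rank-sum.
- Group-by-time: Wilcoxon rank-sum on each child's change from the pre-RM value to T5.

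State which recording is the pre-RM value. The time-point table points to T4c, but the Blinding Procedure refers to T4 as following the maneuver, so the two passages should be reconciled.

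Preferably, run these as sensitivity analyses fixed in advance and drop the normality trigger: tests of normality on about 15 children per group are a weak basis for choosing the method, and the choice is then made after the data are seen. An ANCOVA of T5 on a pre-RM value is an optional alternative for the between-group comparison and is not needed to cure this defect.

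The cost is a sentence or two of text. The tests are standard and available in the named software, and no extra data or patients are needed.
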